**8      General Analysis Considerations****8.1    Analysis Populations****8.1.1    Modified Intention to Treat Population**

All subjects who received any study drug and who participated in at least one post-baseline assessment (i.e., all randomized participants with data following the treatment intervention window).

Participants may be removed from the Modified Intention to Treat Population for analysis if they have (a) no observed data on Post-Intervention assessments, (b) withdrew consent during the study, or (c) were unable to access the online intervention and daily emotion reporting platform.

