Participants in the attention control condition will be prompted to report on positive and negative emotions experienced in the past day and pain level in the past day, going back a maximum of 24 hours. Based on past studies, we expect that this reporting will require approximately 5 minutes per day. Note that participants in the LARKSPUR intervention condition will also be completing the daily reporting of emotions as part of their home practice. The control group will be completing the same number of assessments as the intervention condition at the same time points (baseline, post-intervention, 1-month follow-up).

[figure not shown]
Data collection, transfer, security, and management. Data for the study will come from self-report through online. Self-report data will be collected via online assessment (REDCap) at baseline, during the 6-8-week intervention/control (BrightOutcome), immediate post intervention/control, and at 1-month follow-up. In addition, one week of daily stress and emotion surveys coinciding with each of the three assessments, for a total of 21 days outside the intervention/control period, will be collected via REDCap. The baseline, post-intervention/control, and 1-month follow-up surveys will last 60 and no more than 75 minutes, and may also be done by phone or videoconference in cases of preference, or due to retention follow-up. With participant permission, phone and/or videoconference calls may be recorded for the purpose of accurate data collection. The recordings will be deleted after the study is completed and participation is **not** contingent on the participant's agreement to be recorded. Participants will choose whether or not to authorize recordings when completing their informed consent process.

Data from the online intervention platform will be securely stored on Weill Cornell Medicine and BrightOutcome servers, accessible only to IRB-approved co-investigators and BrightOutcome staff. These data include number of log-ins, completed home exercises, number of skills completed, and data from the daily emotion reporting surveys. All data used for analysis will be de-identified, and no identifiable data will ever be stored locally on staff computers and no data are stored locally on participants' devices.

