## 6.4 Study Assessments

**Table 1.** Schedule of trial events

Table 1: Type and Timing of Measures	PS	B	R	DS	PI	M1
Screening						
Age $\geq$ 50, read and understand English, FMS diagnosis, 6-item self-report	•					
FMS screening tool, cognitive functioning, no other behavioral treatment for pain, internet access, race/ethnicity	•					
Demographic and Clinical Characteristics						
Age, race/ethnicity, sex, income, education, employment, marital status		•				
Charlson Comorbidity Index		•				
Pain						
Standardized Pain Measures		•			•	•
Daily report of pain and fatigue				•		
Physical Function						
Body Mass Index (BMI)		•				
PROMIS Physical Function Short Form 10a		•			•	•
PROMIS Fatigue Short Form 6a		•			•	•
Exercise in the last 24 hrs		•		•	•	•
Psychosocial Factors						
Standardized Psychosocial Factor Measures		•			•	•
Daily stressors (DISE)				•		
Daily positive and negative affect				•		
Daily positive events				•		
Feedback and Care Updates						
Feedback Survey					•	
Self-Enrolled Therapy Update						•

PS = pre-study; B = Baseline; R = randomization; DS = daily survey; PI = Post-Intervention; M1 = 1-Month Follow-Up

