### **8.3 Missing Data**

All missing data due to early discontinuation of participants from the study or otherwise will be handled using mixed-effects modeling (i.e., multilevel modeling) with participant random intercepts. Multilevel models yield unbiased and consistent estimates of model parameters of interest in the presence of missing outcomes under either Missing Completely at Random or Missing at Random missing data mechanisms. Sensitivity to this assumption will be assessed by comparing analytic results using the modified intention to treat sample to complete-case analyses. Complete-case analyses yield unbiased and consistent estimates under a Missing Completely at Random missing data mechanism, although they are less efficient due to the removal of participant data.

Study personnel will make concerted efforts to follow-up with participants that prematurely discontinue participation in the study to understand potential reasons for their discontinuation where possible.

Participant retention and attrition will be summarized at each primary assessment point in the study (Baseline, Post-Intervention, and 1-Month Follow-Up).

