## 10 Efficacy Analyses

All efficacy variables will be summarized by treatment group in accordance with Section 9.

Except for the two Daily Survey Measures [Change in Affective Reactivity to Stress as Measured by the Daily Modified Differential Emotions Scale (mDES) and Change in Affective Reactivity to Stress as Measured by the Daily Inventory of Stressful Events (DISE)], all Secondary Outcomes will be analyzed using mixed-effects analysis of variance with treatment group by time (Post-Intervention, 1-Month Follow-Up) adjusting for the mean-centered Baseline scores on the respective secondary outcome. Models will include fixed effects for treatment (LARKSPUR vs. control), time (Post-Intervention, 1-month Follow-Up), and the interaction between treatment and time. Random intercepts for participants will be included to account for within-participant correlation over time. The modified Intention-to-Treat sample described in Section 8.1 will be used. Treatment groups will be compared at Post-Intervention, at 1-Month Follow-Up, and with respect to their change from Post-Intervention to 1-Month Follow-Up using 2-sided tests at the 5% significance level under the null hypothesis of no difference in means/change. All assumptions for the mixed-effects models will be assessed by inspection of plots of within-participant and between-person residuals. Standard errors, degrees of freedom, 95% confidence intervals, and p-values will be adjusted using the Kenward-Roger method to control the significance level [4]. Restricted maximum likelihood (REML) estimation will be used. All analyses are exploratory with the aim of hypothesis generation as described in the Study Protocol given the pilot nature of this study.

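### The modified ITT rule makes removal of randomised participants optional, including some who can have usable outcomes; a fixed rule costs only wording

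*SAP*

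**What the plan says.** SAP 8.1.1 defines the modified intention-to-treat (mITT) set as subjects given any study drug "who participated in at least one post-baseline assessment (i.e., all randomized participants with data following the treatment intervention window". The next paragraph makes membership conditional: "Participants may be removed from the Modified Intention to Treat Population for analysis if they have (a) no observed data on Post-Intervention assessments". Two further grounds follow in the same sentence, one on consent and one on platform access: "b) withdrew consent during the study, or (c) were unable to access the online intervention and daily emotion reporting platform".

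Other places that bear on this:

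- **Visits.** The schedule legend in SAP 6.4 treats the two post-baseline visits as separate: "PI = Post-Intervention; M1 = 1-Month Follow-Up".
- **Data collection.** Protocol Section 3 (data collection paragraph) says: "Self-report data will be collected via online assessment (REDCap) at baseline, during the 6-8-week intervention/control (BrightOutcome". The Post-Intervention and 1-Month surveys are also REDCap surveys, which "may also be done by phone or videoconference in cases of preference, or due to retention follow-up".
- **Model.** SAP 10 analyses the survey outcomes by "mixed-effects analysis of variance with treatment group by time (Post-Intervention, 1-Month Follow-Up) adjusting for the mean-centered Baseline scores".
- **Missing data.** SAP 8.3 says: "All missing data due to early discontinuation of participants from the study or otherwise will be handled using mixed-effects modeling". Its only stated sensitivity comparison is mITT against complete cases.
- **Use of the set.** SAP 10 and 10.2.1 use mITT for all secondary outcomes, and SAP 10.1 uses it for the two recommendation ratings. Retention (SAP 6.4.1.2) has its own denominators and is not affected.

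**The concern.** An analysis set should follow from the data by a fixed rule. Here three conditions are named, but the word "may" leaves open whether meeting one leads to removal. Nothing says who decides, when, or whether that person is masked to arm and outcome. Participants know their arm (SAP 6.1).

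Two of the three grounds plainly reach people with usable outcomes, and the first does so on one reading. Removing them would take randomised participants out of contrasts that SAP 6.1 says are tested for superiority, for reasons that arise after randomisation.

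The planned safeguards do not cover this. The disposition summaries and CONSORT diagram (SAP 9.1) may count the removals but cannot show their effect on the estimates. The comparison with complete cases does not bring back anyone already dropped from mITT.

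**Working it through.** **1. Each ground against the data collection plan.**

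- *(a) No Post-Intervention data.* If this means any assessment after the intervention, it only restates the entry rule. The SAP, however, uses Post-Intervention as the name of one visit. Read that way, a person with 1-Month data only meets the entry rule and can then be dropped, although the SAP 10 model can use that observation and SAP 8.3 leaves missing visits to the model.
- *(b) Withdrawal of consent.* The ground is not limited to data collected after withdrawal. Someone who withdraws after Post-Intervention can already have a valid outcome.
- *(c) No platform access.* The platform is BrightOutcome, used during the 6-8 weeks. Outcomes come through REDCap, phone or videoconference, so a person who meets (c) can have both outcomes. The ground could act unequally by arm: LARKSPUR needs sequential online lessons, while control reporting is emailed (Protocol Section 3).

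**2. Inputs for the size.** The plan gives no figure to reproduce: no SD, effect size or expected number of removals.

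- From the documents: 45 per arm (SAP 7) and 75 per arm (Protocol Section 3). These disagree, so both are used. Past retention with the control condition is about 80% (Protocol Section 3).
- Assumed: 80% complete Post-Intervention in each arm; 90% of those complete 1-Month; within-person correlation ρ = 0.5; removals of 1, 2 or 4 per arm.
- Observed per arm: 45 × 0.8 = 36, then 36 × 0.9 ≈ 32; 75 × 0.8 = 60, then 60 × 0.9 = 54.

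**3. Precision.** Per-arm information for the two visit means is n11·S⁻¹ + diag(n10, 0) + diag(0, m). Here S is the 2×2 correlation matrix, n11 the number with both visits, n10 the number with Post-Intervention only, and m the number with 1-Month only. V is the matching diagonal element of the inverse, and the 95% half-width in residual SD units is 1.96·√(2V).

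*Ground (a), 1-Month contrast.* At 45 per arm (n11 = 32, n10 = 4) the half-width is 0.483 with m = 0, and 0.476, 0.469 and 0.456 with m = 1, 2 and 4. At 75 per arm (n11 = 54, n10 = 6) it is 0.372, against 0.369, 0.366 and 0.360.

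*Grounds (b) and (c).* Replace n11 by n11 − r. For Post-Intervention this reduces to √(36/(36 − r)) − 1 or √(60/(60 − r)) − 1.

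| Widening of 95% CI | 1 per arm | 2 per arm | 4 per arm |
|---|---|---|---|
| (a), 1-Month, 45 per arm | 1.5% | 3.0% | 5.9% |
| (a), 1-Month, 75 per arm | 0.9% | 1.8% | 3.5% |
| (b)/(c), Post-Intervention, 45 per arm | 1.4% | 2.9% | 6.1% |
| (b)/(c), 1-Month, 45 per arm | 1.6% | 3.2% | 6.7% |
| (b)/(c), Post-Intervention, 75 per arm | 0.8% | 1.7% | 3.5% |
| (b)/(c), 1-Month, 75 per arm | 0.9% | 1.9% | 3.8% |

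With ρ = 0.7 and 45 per arm, the 1-Month figures change little: 1.5%, 2.9% and 5.7% for (a); 1.5%, 3.1% and 6.5% for (b)/(c).

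**4. Bias.** It is zero if removals are balanced and those removed differ from the rest equally in each arm. One extra removal from one arm, of someone k T-score points worse after baseline adjustment, shifts the Post-Intervention contrast by k/n. Assume SD 10 and baseline correlation 0.5. The half-width is then 1.96 × 10 × √(2/36) × √0.75 = 4.00 points, or 3.10 points with 60 observed.

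| k (points) | Shift, 36 observed | Share of 4.00 | Shift, 60 observed | Share of 3.10 |
|---|---|---|---|---|
| 2.5 | 0.07 | 1.7% | 0.04 | 1.3% |
| 5 | 0.14 | 3.5% | 0.08 | 2.7% |
| 10 | 0.28 | 6.9% | 0.17 | 5.4% |

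**5. Upper limit from optional removal.** Three optional grounds allow 2³ = 8 analysis sets. In 20,000 simulated null trials, each ground flagged 2%, 5% or 10% of participants independently of outcome, and the most favourable set was always chosen. Type I error was 6.9%, 8.0% and 10.2% with 36 per arm, and 6.8%, 8.5% and 10.5% with 60. Under a fixed rule, whether keep all or drop all, it stayed near 5%. This is a worst case; nothing in the documents suggests such selection.

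**The case against.** The other side has several fair points.

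- **The wording may only list reasons.** SAP 9.1 uses "may" in that way for attrition. But 8.1.1 still does not say whether removal is automatic.
- **Ground (a) may be empty.** SAP 6.4.1.2 defines 1-Month retention only among Post-Intervention completers, and nothing shows that anyone will have 1-Month data only. Four such people per arm would be 4 of the 9 assumed to miss Post-Intervention at 45 per arm. This stands, so the point rests mainly on (b) and (c).
- **Ground (b) turns on consent terms**, which are not in the text reviewed. This also stands, and the fix has to defer to them.
- **Ground (c) is a natural online counterpart of having received treatment**, in a set openly labelled modified. Daily internet access is an inclusion criterion, so cases should be few. That explains the ground, but removing people for not receiving their allocation is what an ITT-type set is meant to avoid.
- **The analyses are exploratory** (SAP 10) and the trial is not powered for outcomes (SAP 4.2). That limits the severity. Effect size is nevertheless a stated objective, and the two ratings are primary outcomes.
- **The simulated 7% to 10% overstates the risk at Post-Intervention.** There, ground (a) removes nobody with an outcome, so at most four sets exist; with two grounds the error is about 6% to 8%. This is accepted.

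**Conclusion.** The concern holds as a minor point. Followed as written, SAP 8.1.1 can drop randomised people with usable outcomes, and no planned analysis restores them. High confidence applies to the wording and to grounds (b) and (c); ground (a) depends on how the visit name is read.

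The expected effect is small: at most about 7% on interval width and under 0.3 T-score point for one extra one-arm removal, across the ranges shown. These figures depend on assumed retention, correlation, SD and counts. Whether any removal would occur, or would differ by arm, cannot be told from the documents. The case for change is that the remedy is cheap, not that damage is likely.

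**What to change.** In SAP 8.1.1:

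- Define the set for the secondary outcomes as all randomised participants, analysed as randomised, with any Post-Intervention or 1-Month outcome.
- Delete the reference to study drug, which does not exist in this behavioural trial, together with the optional-removal wording and grounds (a) and (c).
- For (b), keep data collected before withdrawal where consent permits.
- For the two recommendation ratings, state a separate fixed rule, such as all LARKSPUR participants who completed the feedback survey, and report platform access alongside.
- Fix and date the wording before outcomes are seen by arm.

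The cost is wording only: sample size, alpha, schedule and data collection do not change. The downside is some dilution of the secondary estimates from people who could not use the platform. The daily-measure model also takes Baseline as an outcome time (SAP 10.2.1), so this rule leaves out participants with Baseline daily data only; they add almost nothing to the treatment contrasts.

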**8.2    Covariates and Subgroups**

Baseline covariates for each secondary outcome are expected to correlate with their matching secondary outcome scores at Post-Intervention and 1-Month Follow-Up assessments. Therefore, analyses of each secondary outcome will include participant Baseline scores for adjustment of superiority analyses of treatment differences.

Race/ethnicity was used to stratify treatment allocation and will be adjusted for in primary analyses if sample sizes within each race/ethnicity—treatment subgroup is sufficient (i.e., greater than 5). Otherwise, race/ethnicity will be omitted from primary analyses.

Given the pilot nature of the study, sample size was chosen based on feasibility indicators (recruitment, retention, adherence) rather than on formal power calculations [see 1]. Accordingly, interaction analyses comparing treatment effects by race/ethnicity, age and gender are exploratory.

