### 10.1 Primary Efficacy Analysis

The Recruitment Primary Outcome will be calculated as described in Section 6.4.

The Retention Primary Outcome treatment group percentages will be compared using Boschloo's Test at the 2-sided 5% significance level under the null hypothesis that retention rates are equal between treatment groups [15]. The maximum likelihood estimate of the odds ratio of treatment retention to control retention will be computed with a 2-sided 95% confidence interval and p-value.

The Rating of Recommending Intervention to Friend and Rating of Recommending Intervention to Those with Chronic Pain items will be summarized using an ordinal regression (proportional odds) model without predictors (i.e., the ordinal properties of the Likert scales of these two items will be respected by estimating the average rating adjusted for the cumulative category response probability distribution) [16]. The modified Intention-to-Treat sample described in Section 8.1 will be used.

The Length of Intervention Time will be calculated as described in Section 6.4.

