## 10.2 Secondary Efficacy Analyses

Exploratory interaction analyses along demographic (ethnicity, race) and clinical covariates will assess treatment effect heterogeneity for the primary outcome analyses in Section 10.1 by summarizing/testing Primary Outcomes by subgroup.

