### 10.2.1 Analyses of Secondary Endpoints

Secondary Outcomes will be analyzed as described in Section 10 for the eight survey assessment measures detailed in Section 6.4.2.

The Change in Affective Reactivity to Stress as Measured by the Daily Modified Differential Emotions Scale (mDES) measure and the Change in Affective Reactivity to Stress as Measured by the Daily Inventory of Stressful Events (DISE) will be analyzed using mixed-effects analysis of variance with treatment group by time (Baseline, Post-Intervention, 1-Month Follow-Up) by day in burst (1, 2, ..., 7). Models will include fixed (linear) effects for treatment (LARKSPUR vs. control), time (Baseline, Post-Intervention, 1-month Follow-Up), day in burst, and the interactions between treatment group, time, and day in burst. Random intercepts for participants and random slopes for linear day in burst effects will be included to account for within-participant correlation over time. The modified Intention-to-Treat sample described in Section 8.1 will be used. Treatment groups will be compared at Post-Intervention, at 1-Month Follow-Up, and with respect to their change from Post-Intervention to 1-Month Follow-Up using 2-sided tests at the 5% significance level under the null hypothesis of no difference in means/change. All assumptions for the mixed-effects models will be assessed by inspection of plots of within-participant and between-person residuals. Standard errors, degrees of freedom, 95% confidence intervals, and p-values will be adjusted using the Kenward-Roger method to control the significance level [4]. Restricted maximum likelihood (REML) estimation will be used. All analyses are exploratory with the aim of hypothesis generation as described in the Study Protocol given the pilot nature of this study.

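### SAP 8.2 promises adjustment for the randomisation stratifier in undefined primary analyses, the model sections do not list it, and the cell-count rule does not say when cells are counted (minor)

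*SAP*

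**What the plan says.** **Adjustment.** SAP 8.2 recalls that race/ethnicity stratified the allocation and says it "will be adjusted for in primary analyses if sample sizes within each race/ethnicity—treatment subgroup is sufficient (i.e., greater than 5"; if not, it is left out. The same section separately commits to adjusting each secondary outcome for its Baseline score.

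**Models.** SAP 10 specifies the survey-outcome model as "adjusting for the mean-centered Baseline scores on the respective secondary outcome" and then states: "Models will include fixed effects for treatment (LARKSPUR vs. control), time (Post-Intervention, 1-month Follow-Up), and the interaction between treatment and time". SAP 10.2.1 does the same for the daily measures: "Models will include fixed (linear) effects for treatment (LARKSPUR vs. control), time (Baseline, Post-Intervention, 1-month Follow-Up), day in burst", plus interactions. Both sections refer to Section 8.1 for the analysis population. Neither refers to 8.2 or mentions race/ethnicity.

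**Primary outcomes.** SAP 10.1 compares retention by Boschloo's test, adds a maximum likelihood odds ratio with no covariate stated, and summarises the two recommendation items by an "ordinal regression (proportional odds) model without predictors". SAP 6.1 says primary outcomes other than retention are not tested.

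**Heterogeneity.** SAP 8.2: "Accordingly, interaction analyses comparing treatment effects by race/ethnicity, age and gender are exploratory". SAP 10.2: "Exploratory interaction analyses along demographic (ethnicity, race) and clinical covariates" "will assess treatment effect heterogeneity for the primary outcome analyses in Section 10.1". Objective 5.1.1.2 mentions exploring racial/ethnic disparities in the same sentence as pain and the secondary outcomes.

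**The concern.** A covariate promise needs a model to sit in. Here the nearest heading to the phrase in 8.2 is Section 10.1, whose methods as written use no covariate. The models where adjustment would help do not name the stratifier. An analyst working from Section 10 alone would omit it, and one who reads 8.2 as general guidance would include it. Both could claim to follow the SAP.

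The threshold adds a second choice. The SAP does not say whether cells are counted as randomised, in the modified intention-to-treat sample, or among those observed at a visit. These counts can fall on different sides of 5.

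At stake are a little precision and, more importantly, whether the model is fixed in advance. The subgroup factors also differ between 8.2 (race/ethnicity, age, gender) and 10.2 (ethnicity, race, unspecified clinical covariates).

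**Working it through.** The SAP gives no figure on this point to reproduce. The checks below size the consequences.

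**Inputs from the documents.** Three strata by two arms gives six cells (SAP 6.3). Planned size is 45 per arm (SAP 7) or 75 per arm (Protocol 3). The recruitment target is equal thirds (Protocol 4.4). Past retention in the control condition was about 80% (Protocol 3). SAP 7 plans 45 to secure 30 per arm, an implied loss of 1 − 30/45 = 33%.

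**Assumed, not in the documents.** R², the share of outcome variance left after Baseline that race/ethnicity explains: 2%, 5%, 10%. A 60/20/20 stratum split as an alternative to equal thirds. Balanced or simple allocation within strata, because the documents do not say whether blocks are used.

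**1. Cost of omitting the stratifier (single time point).** If arms are balanced within strata, the unadjusted SE is too wide by 1/√(1 − R²), and the true two-sided error rate is 2[1 − Φ(1.96/√(1 − R²))].

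| R² | SE ratio | Type I error |
|---|---|---|
| 2% | 1.010 | 0.048 |
| 5% | 1.026 | 0.044 |
| 10% | 1.054 | 0.039 |

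A simulation with 45 per arm and 40,000 runs per setting agreed: SE ratios 1.011, 1.027, 1.055 and error rates 0.048, 0.044, 0.039. Under simple randomisation within strata the unadjusted error rate stayed at 0.049 to 0.050, and the unadjusted estimate's SD was 0.0%, 1.3% and 4.3% larger than the adjusted one's. The adjusted analysis held 0.048 to 0.051 throughout. Two extra degrees of freedom raise the critical t by 0.03% with 90 analysed and 0.05% with 72.

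**2. The greater-than-5 rule.** A stratum needs at least 6 + 6 = 12 people, which is 12/90 = 13.3% of the sample at 45 per arm. The table gives the probability that at least one of the six cells is 5 or fewer, so that the term is dropped. Stratum totals were drawn multinomially, arms were split within strata, and loss was binomial (400,000 runs).

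| Per arm, stratum shares | Cells counted | Balanced | Simple |
|---|---|---|---|
| 45, equal thirds | at randomisation | 0% | 0.9% |
| 45, equal thirds | after 20% loss | 1.3% | 8.6% |
| 45, equal thirds | after 33% loss | 13.6% | 31% |
| 45, 60/20/20 (assumed) | at randomisation | 7.5% | 37% |
| 45, 60/20/20 (assumed) | after 20% loss | 52% | 74% |
| 75, equal thirds | any of the above | at most 0.02% | at most 0.3% |

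At the SAP's planned size, when the cells are counted can therefore decide which model is fitted. At the protocol's size and target it hardly matters.

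**3. What stratum-specific estimates could show.** With 36 analysed per arm (45 × 0.8), 12 per cell and t(66) = 1.997, the 95% half-widths in residual SD units are:
- overall: 1.997 × √(2/36) = 0.47
- one stratum: 1.997 × √(2/12) = 0.82
- difference between two strata: 1.997 × √(4/12) = 1.15

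With 60 per arm, 20 per cell and t(114) = 1.981, they are 0.36, 0.63 and 0.89.

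**The case against.** **Section 8 is general guidance.** Its heading says so, and the fixed-effects sentence in Section 10 is not exhaustive: Baseline is absent from it too, and enters through the sentence before. So the missing term does not prove that the SAP excludes it, and a reader who infers that the SAP contradicts itself goes too far. What stands is that Section 10 restates one of 8.2's two covariate commitments and not the other, with no reference back.

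**Section 10.1 could carry a covariate.** The retention odds ratio could be adjusted, and 10.2 uses similar wording for the feasibility outcomes. It would therefore be wrong to say the promise cannot be carried out there. As written, though, no 10.1 analysis uses it, so the authors need to say what they meant.

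**The coding of race/ethnicity.** A reader might infer that it is open because SAP 9.2.1 lists race and ethnicity separately. For adjustment that does not hold: 8.2 ties the variable to the stratifier, and 9.2.1 is descriptive. The looseness is confined to 10.2.

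**The disparities objective.** A reader might infer that a promised interaction analysis is missing for every secondary outcome. Objective 5.1.1.2 only speaks of exploring disparities, and SAP 4.2 frames the trial around feasibility in a diverse sample, which fits 10.2.

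**Everything affected is exploratory.** SAP 10 and 10.2.1 say so, and SAP 7 urges caution on subgroups. This is fair and keeps the point minor. It does not remove the need to say which model is fitted.

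**Conclusion.** The point holds as a minor one. The SAP leaves open whether the stratifier enters the secondary-outcome models and when the rule that governs it is applied.

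Leaving it out costs up to about 5% in standard error at an assumed residual R² of 10%, and less at smaller values. The conservatism depends on within-stratum balance, which the documents do not state. A reader might infer that omitting a stratifier inflates false positives; on neither allocation scheme does it. The precision figures are for one time point and were not derived for the repeated-measures or daily models.

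The counting rule has the larger effect on which model is fitted. At 45 per arm, the chance of dropping the term goes from 0% to 74% across the settings shown. The upper end rests on the assumed 60/20/20 split and simple randomisation; with the equal-thirds target it does not exceed 31%.

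**What to change.** 1. In SAP 10 and 10.2.1, add the three-level race/ethnicity stratifier as an additive fixed effect in the secondary-outcome mixed models. In 8.2, name those models in place of the undefined term. If the authors meant the retention odds ratio in 10.1, they should say so.
2. Delete the greater-than-5 rule, or state that cells are counted at randomisation.
3. Make the heterogeneity factors in 8.2 and 10.2 agree, using the three-level variable for race/ethnicity.
4. Optionally, because objective 5.1.1.2 places disparities with pain, report exploratory stratum-specific effects with 95% intervals for pain intensity and interference only, labelled descriptive given the widths above.

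Items 1 to 3 are SAP wording. The additive term costs 2 degrees of freedom per model and no new data, since race/ethnicity is already on the assessment schedule. Boschloo's test for retention is unchanged.
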